## **7.9. Pharmacokinetic Assessments**

In Stage 2, samples for pharmacokinetic analysis will not be collected. Pentraxin-2 levels will be drawn prior to each dose for pharmacodynamic assessment and correlation with potential anti-pentraxin 2 antibodies.

## **7.10. Exploratory Laboratory Assessments**

At time points throughout the study, as indicated in the Schedule of Events ([APPENDIX A](#)), blood samples will be collected and DNA will be isolated from peripheral whole blood for the purpose of associating baseline mutational status with select primary and secondary endpoints. DNA sampling is not mandatory for subjects. Subjects can still enroll in the trial if they opt out of DNA sampling. Samples will be analyzed for cytogenetic abnormalities and for mutations JAK2V617F, MPLW515, Calreticulin, ASXL1, EZH2, SRSF2, IDH1/2. Samples will also be analyzed to assess changes in the allele burden of JAK2V617F at week 36 (Cycle 1 Day 1 to Cycle 9 Day 29). These samples will also be analyzed to assess changes in the allele burden of MPLW515, Calreticulin, ASXL1, EZH2, SRSF2, IDH1/2 at week 36 (Cycle 9, Day 29) as quantitative assays become commercially available.

Additional assays may be performed that contribute to the objectives of the trial. Additional bone marrow biopsy slides will be collected for immunohistochemical analysis for disease and mechanism related proteins and cellular markers.

Sample handling details will be provided.

## **7.11. Efficacy Assessments**

The following efficacy assessments, in addition to some of the safety assessments described in 7.12 will be performed.

### **7.11.1 Bone Marrow Biopsy**

Bone marrow biopsy will be performed at screening, Cycle 4, Day 1, Cycle 7, Day 1, and Cycle 9, Day 29. Analysis will include confirmation of diagnosis and assessments of reticulin stain and trichrome stain. Slides will be sent to a central committee of hematopathologists who will be

blinded to subject, treatment, and collection time for centralized grading of fibrosis. A charter will be established for the central committee. Quantification of marrow fibrosis will be performed in a blinded fashion by computer assisted image analysis. Unstained slides will be collected for analysis of disease and mechanism related changes.

#### **7.11.2 Assessment of transfusions**

Subjects will be required to enter all RBC and platelet transfusion in a transfusion diary, which will be reviewed at each visit. Data will be entered in the eCRF.

#### **7.11.3 Assessment of spleen size**

##### **7.11.3.1. Palpation**

During the physical examination, the spleen will be measured in centimeters below the left costal margin and recorded in the eCRF.

##### **7.11.3.2. Imaging**

On Cycle 1 Day 1, Cycle 4 Day 1, Cycle 7 Day 1, and Cycle 9 Day 29, CT or MRI will be used to measure spleen volume in all subjects. For subjects who receive PET-CT imaging as described in 7.11.5, the PET-CT will be used to assess spleen volume and subjects will not require additional imaging.

#### **7.11.4 Assessment of Symptoms**

##### **7.11.4.1 Myeloproliferative Neoplasm Symptom Assessment Form (MPN-SAF)**

The Myeloproliferative Neoplasm Symptom Assessment Form (MPN-SAF) will be administered to evaluate the effects of PRM-151 treatment on subject quality of life (QOL) ([APPENDIX G](#)).

##### **7.11.4.2. EORTC QLQ-C30**

The EORTC QLQ-C30 will be administered to evaluate the effects of PRM-151 treatment on subject quality of life (QOL) ([APPENDIX H](#)).

##### **7.11.5. FDG or FLT PET-CT Imaging**

At sites where it is feasible, FDG or FLT PET-CT scans will be done to assess changes in metabolism of bone marrow, spleen, and liver at Cycle 1 Day 1, Cycle 4 Day 1, Cycle 7 Day 1 and Cycle 9 Day 29. Subjects receiving PET-CT imaging will not require additional CT or MRI scans as described in 7.11.3.2.

##### **7.11.6. Response Assessments**

Subjects will be assessed for response at Cycle 2 through Cycle 9. Response Assessments are based on International Working Group-Myeloproliferative Neoplasms Research and Treatment (IWG-MRT) criteria, to measure the overall response rate (ORR), defined as a clinical improvement (CI), partial remission (PR), and complete remission (CR) according to the International Working Group (IWG) Criteria ([APPENDIX B](#)).

## 7.12. Safety Assessments

### 7.12.1. Physical Examination

Abbreviated physical examinations will be performed by the Investigator and will include a review of the subject's general appearance as well as evaluation of the following body systems ([Table 1](#)). Any abnormal change in findings after exposure to the study drug will be recorded as an adverse event (AE) on the appropriate eCRF.

**Table 1: Assessments for Physical Examinations**

Assessment	Assessment
General appearance	Throat
Head and neck	Cardiovascular
Eyes	Abdomen
	Chest and lungs

### 7.12.2 Vital Signs

Vital signs, including pulse, temperature (oral, temporal, or tympanic), respiration rate, and systolic and diastolic blood pressure will be measured and recorded on the eCRF.

### 7.12.3. Clinical Laboratory Tests

Blood samples will be collected for clinical laboratory testing and sent to a central laboratory as listed below. In the event the central lab cannot be used to get a reliable result for a laboratory test, local laboratory tests may be used after this has been agreed upon by the Medical Monitor.

**Table 2: Clinical Laboratory Tests**

#### Clinical Chemistry:

- Sodium
- Bicarbonate
- Glucose
- Aspartate transaminase (AST)
- Alkaline phosphatase
- Uric acid
- Potassium
- Calcium
- Albumin
- Alanine aminotransferase (ALT)
- Creatine phosphokinase (CPK)
- Chloride
- Creatinine
- Phosphorus
- Bilirubin, direct and indirect
- Lactate dehydrogenase (LDH)
- Blood urea nitrogen (BUN)
- Serum pregnancy test

- Urine pregnancy test (local lab)

#### **Hematology:**

- Hemoglobin
- Hematocrit
- Platelets
- White Blood Cell (WBC) with differential
- Red Blood Cell (RBC)
- Reticulocyte count
- Blast count
- Absolute Neutrophil (ANC)
- Partial thromboplastin time (PTT)
- Prothrombin time (PT)
- International normalized ratio (INR)
- Nucleated red blood cells, immature cells, and other leukoerythroblastic changes

For subjects receiving warfarin, the PT, PTT and international normalized ratio (INR) must be obtained. Abnormal INRs will be tested twice weekly until the INR is stable for one month, followed by monthly monitoring of the INRs.

#### **7.12.4. Pregnancy Test**

A serum  $\beta$ -hCG pregnancy test will be performed for women of childbearing potential within 4 weeks prior to dosing on Cycle 1 Day 1. The serum pregnancy test will be sent to a central laboratory for testing and the results must be available and negative before dosing. Pregnancy testing is not required for postmenopausal or surgically sterilized women. Urine pregnancy test will be performed at the local lab thereafter, as indicated in Schedule of Events table in [APPENDIX A](#).

#### **7.12.5. Electrocardiograms (ECG) Assessments**

Electrocardiograms (ECG) Assessments will be performed at screening and in the event of an infusion reaction.

#### **7.12.6. Immune Response Assessments**

Blood samples (4 mL) will be collected prior to each dose of PRM-151 to measure antibodies to PTX-2. In addition, if a subject experiences an acute infusion related reaction, a blood sample will be collected for cytokines and antibodies against PRM-151. A blood sample for cytokines and antibodies against PRM-151 may be obtained in the event of a suspected adverse reaction. All samples collected may not be analyzed.

#### **7.12.7. Sample Collection, Storage, and Shipping**

Detailed instructions for laboratory sample collection, processing, and shipping instructions will be provided. All samples for exploratory assessments from the study will be stored at – 80C.

### **7.13. Adverse Events Assessments**

#### **7.13.1 Definitions of Adverse Events and Serious Adverse Events**

### 7.13.1.1 Adverse Event

An AE is any noxious, pathologic, or unintended change in anatomical, physiologic, or metabolic function as indicated by physical signs, symptoms, or laboratory changes occurring in any phase of a clinical study, whether or not considered investigational product-related. This includes an exacerbation of a pre-existing condition.

Adverse events include:

- Worsening (change in nature, severity, or frequency) of conditions present at the onset of the study;
- Intercurrent illnesses;
- Drug interactions;
- Events related to or possibly related to concomitant medications;
- Abnormal laboratory values (this includes significant shifts from baseline within the range of normal that the Investigator considers to be clinically important);
- Clinically significant abnormalities in physical examination, vital signs, and weight.

Throughout the study, the Investigator must record all AEs on the AE eCRF, regardless of the severity or relationship to investigational product. The Investigator should treat subjects with AEs appropriately and observe them at suitable intervals until the events stabilize or resolve. Adverse events may be discovered through observation or examination of the subject, questioning of the subject, complaint by the subject, or by abnormal clinical laboratory values.

In addition, AEs may also include laboratory values that become significantly out of range. In the event of an out-of-range value, the laboratory test should be repeated until it returns to normal or can be explained and the subject's safety is not at risk.

Additional illnesses present at the time when informed consent is obtained are regarded as concomitant illnesses and will be documented on the appropriate pages of the eCRF. Illnesses first occurring or detected during the study, and worsening of a concomitant illness during the study, are to be regarded as AEs and must be documented as such in the CRF.

Infusion reactions were reported in two subjects in Stage 1 of this study. In the event of acute hypersensitivity or other infusion reaction, institutional protocol should be initiated and a blood sample drawn for anti-PTX-2 antibodies and cytokines. Signs and symptoms of an infusion reaction may include the following: headache, fever, facial flushing, pruritus, myalgia, nausea, chest tightness, dyspnea, vomiting, erythema, abdominal discomfort, diaphoresis, shivers, hypertension, hypotension, lightheadedness, palpitations, urticaria and somnolence. Although unlikely, serious allergic reactions (e.g., anaphylaxis) may occur at any time during the infusion.

In the case of Grade 2 occurrence of signs and symptoms consistent with infusion related reaction, follow institutional protocol and reduce the rate of infusion of PRM-151 to half the initial rate; consider discontinue infusion of PRM-151 if symptoms do not respond to medical intervention. If

signs and symptoms resolve with intervention including discontinuation of PRM-151, PRM-151 infusion may be restarted at half the initial rate.

In the case of Grade 3 or greater occurrence of signs and symptoms consistent with infusion related reaction, discontinue infusion of PRM-151.

If PRM-151 resulted in signs and symptoms consistent with Grade 2 or 3 Infusion related reaction, infuse PRM-151 over 1 hour and use the following premedication for all subsequent PRM-151 administration:

- a. Diphenhydramine 50 mg IV or clemastine 2 mg IV or an equivalent dose of an antihistaminic drug
- b. Dexamethasone 10 mg IV or an equivalent corticosteroid

Infusion related reactions must be reported to Promedior as described in section 7.13.2.1.1, Reporting of Adverse Events of Special Interest.

#### **7.13.1.2. Serious Adverse Event**

A serious AE (SAE) is any AE occurring at any dose that results in any of the following outcomes:

- Death;
- Is life-threatening;
- Requires hospitalization;
- Requires prolongation of existing hospitalization;
- A persistent or significant incapacity or substantial disruption of the ability to conduct normal life functions;
- A congenital anomaly or birth defect;

Important medical events that may not result in death, be life-threatening, or require hospitalization may be considered an SAE when, based upon appropriate medical judgment, they may jeopardize the subject and may require medical or surgical intervention to prevent one of the outcomes listed in this definition. A life-threatening AE is defined as an AE that placed the subject, in the view of the initial reporter, at immediate risk of death from the AE as it occurred (i.e., it does not include an AE that, had it occurred in a more severe form, might have caused death).

#### **7.13.1.3. Classification of Adverse Events and Serious Adverse Events**

The National Cancer Institute Common Terminology Criteria for Adverse Events (NCI-CTCAE) Version 4.0 grading scale ([APPENDIX I](#)) should be referenced when assessing the intensity of an AE. If an AE is not described in the NCI CTCAE v 4.0, the severity should be recorded based on the scale below. The severity of all AEs/SAEs should be recorded on the appropriate eCRF page as Grade 1, 2, 3, or 4 corresponding, respectively, to a severity of mild, moderate, severe, or life threatening as outlined in [Table 3](#).

[http://www.eortc.be/services/doc/ctc/CTCAE\\_4.03\\_2010-06-14\\_QuickReference\\_5x7.pdf](http://www.eortc.be/services/doc/ctc/CTCAE_4.03_2010-06-14_QuickReference_5x7.pdf)

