**Table 3: Adverse Event Grading**

Severity	Definition
Grade 1	Mild; asymptomatic or mild symptoms, clinical or diagnostic observations only; intervention not indicated.
Grade 2	Moderate; minimal, local or noninvasive intervention indicated; limiting age-appropriate instrumental ADL.
Grade 3	Severe or medically significant but not immediately life-threatening; hospitalization or prolongation of hospitalization indicated; disabling; limiting self care ADL.
Grade 4	Life-threatening consequences; urgent intervention indicated.
Grade 5	Death related to AE.

**Clarification between Serious and Severe:** The term “severe” is often used to describe the intensity (severity) of a specific event (as in mild, moderate, or severe myocardial infarction); the event itself, however, may be of relatively minor medical significance (such as severe headache). This is not the same as “serious,” which is based on the outcome or action criteria usually associated with events that pose a threat to life or functioning. Seriousness (not severity) and causality serve as a guide for defining regulatory reporting obligations.

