### **10.6.2. Safety Analysis**

Safety evaluations will be based on the incidence, intensity, and type of adverse events, and clinically significant changes in the subject's physical examination, vital signs and clinical laboratory results. Safety variables will be tabulated and presented for all subjects who receive any amount of study medication. Exposure to study drug and reasons for discontinuation of study treatment will be tabulated.

Adverse events will be coded using the Medical Dictionary for Regulatory Activities (MedDRA) adverse event coding system for purposes of summarization. All adverse events occurring on study will be listed in by-subject data listings. Treatment-emergent events (TEAEs) will be tabulated, where treatment-emergent is defined as any adverse event that occurs after administration of any amount of study drug, or any event that is present at baseline but worsens in intensity or is subsequently considered drug-related by the Investigator. By treatment tabulations will be performed by MedDRA system organ class (SOC) and preferred term (PT) for deaths if any, serious adverse events; all treatment-emergent adverse events; TEAEs leading to discontinuation of study therapy due to adverse event or toxicity and TEAEs resulting in study discontinuation. Events that are considered related to treatment (possibly or probably drug-related) will also be tabulated. Tabulation will also be provided that enumerates adverse events by maximum severity.

Laboratory evaluations will be summarized by time of collection and by treatment group. In addition, change from baseline to any post-dose values will be summarized for vital signs and clinical laboratory results.

The frequency of subjects with abnormal safety laboratory results will be tabulated by treatment. Shift tables for each cycle will be produced for selected laboratory parameters, to include at least hemoglobin, WBC count, neutrophils, lymphocytes, platelets, AST, ALT, bilirubin, LDH, creatinine, alkaline phosphatase and electrolytes. These tables will summarize by cycle and dose level the number of subjects with each baseline CTC grade and changes to the maximum CTC grade in the cycle.

Clinically significant laboratory abnormalities will be tabulated or presented in individual data listings, depending on their number.

Vital signs assessments will be summarized over time in a similar fashion to laboratory parameters, and any abnormal values will be tabulated.

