**APPENDIX I: National Cancer Institute Common Terminology Criteria for Adverse Events (NCI CTCAE)**

The United States of America (USA) National Cancer Institute Common Terminology Criteria for Adverse Events, version 4.0 (NCI CTCAE, v.4.0) can be found on the following website.

[http://ctep.cancer.gov/protocolDevelopment/electronic\\_applications/ctc.htm#ctc\\_40](http://ctep.cancer.gov/protocolDevelopment/electronic_applications/ctc.htm#ctc_40)

[Accessed: 13 February 2013]

This version of CTCAE is compatible at the AE (Adverse Event) term level where each CTCAE term is a Medical Dictionary for Regulatory Activities Terminology (MedDRA) LLT (Lowest Level Term). CTCAE v4.0 includes 764 AE terms and 26 'Other, specify' options for reporting text terms not listed in CTCAE. Each AE term is associated with a 5-point severity scale. MedDRA v12.0.

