4.7 SAFETY ANALYSES

The safety analysis population will be used for all safety analyses. Analyses will be performed for both stages separately, as well as for the OLE phases.

4.7.1 Exposure to Study Medication

Information on study drug administration will be summarized by duration, starting dose, and cumulative dose. In addition, treatment exposure will be summarized, including the percentage of the planned dose given at each cycle.

Withdrawals of subjects from study treatment will be reported as listings and summary tables.

4.7.2 Adverse Events

Coding of all adverse events will be done using the latest version of the Medical Dictionary for Regulatory Activities (MedDRA). As part of the safety data transfer to Roche, the adverse events will be re-coded in legacy coding domain after database lock. Consequently, no queries are planned to be raised for any discrepancies in MedDRA Preferred Terms (PTs). This might result in some event terms that are vague (for example - 'heart problems') to be coded to less accurate, more high level concepts (eg Cardiac disorder for the example given). All AEs and routine laboratory parameters will be assessed according to the National Cancer Institute Common Terminology Criteria for Adverse Event (NCI CTCAE) version 4.0 grading system.

For AEs, the most extreme intensity will be used for reporting. All AEs occurring during or after the first treatment will be described by summary tables divided by body system, NCI CTCAE grade, and relation to study treatment. In tables showing the overall incidence of AEs, subjects who experienced the same event on more than one occasion are counted only once in the calculation of the event frequency and the AE with the most extreme severity will be included.

For selected events of particular interest (Infusion Related Reaction[IRR]) more detailed analyses will be conducted. The analyses will depend on the specific question of interest for that particular AE. IRR will be presented by anti-drug antibody status. In addition, the IRR event frequency and severity will be included in the analysis. Treatment discontinuations due to IRR will be listed.

AE leading to treatment discontinuations and early study withdrawals will be summarized by treatment group and by reason. In addition, all serious AE will be summarized.

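### The instruction to record every adverse event as Grade 1 to 4 conflicts with the Grade 5 row of Table 3 and the 5-point CTCAE scale, so the severity tables may understate Grade 5 and disagree with the death tabulations

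*Protocol*

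**What the plan says.** Protocol Section 7.13.1.3 makes CTCAE v4.0 the grading reference, which "should be referenced when assessing the intensity of an AE". Table 3 is the fallback for events that CTCAE does not describe. The section then says what is to be entered: "The severity of all AEs/SAEs should be recorded on the appropriate eCRF page as Grade 1, 2, 3, or 4 corresponding, respectively". The four grades are matched in order to four severity words, of which the last is life threatening, and the sentence refers the reader to Table 3.

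Table 3 follows directly and has five rows. The last is Grade 5, defined as "Death related to AE". Appendix I says of CTCAE v4.0: "Each AE term is associated with a 5-point severity scale".

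The grade is used in two planned analyses:

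- Protocol 10.6.2: "Tabulation will also be provided that enumerates adverse events by maximum severity".
- SAP 4.7.2: "For AEs, the most extreme intensity will be used for reporting". Its adverse event tables are divided by body system, CTCAE grade and relation to treatment.

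Deaths are also reported separately. Protocol 10.6.2 states: "By treatment tabulations will be performed by MedDRA system organ class (SOC) and preferred term (PT) for deaths if any". SAP 4.7.2 summarises deaths on treatment and in follow-up by treatment group.

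**The concern.** The recording sentence covers all adverse events, serious ones included, and its list closes at four grades, each tied in order to a severity word. Death is the first seriousness criterion in Section 7.13.1.2, so the rule covers events whose outcome it cannot express. A site that follows the sentence enters a fatal event as Grade 4. A site that follows the table or CTCAE enters Grade 5.

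The safety and tolerability of three doses is a secondary objective (Section 2.2), and the worst-grade tables are one of the displays that serve it. If fatal and survived life-threatening events share a row, or are split differently by site, a comparison of doses on Grade 4 against Grade 5 is unreliable. A report could also show deaths in one table and no Grade 5 events in another, with no stated way to reconcile them.

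**Working it through.** The plan states no figure to reproduce. The check is a comparison of the texts, followed by bookkeeping on what a shifted grade does to a table.

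**Grades available at each place**

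| Place | Grades | Top grade |
|---|---|---|
| Protocol 7.13.1.3, recording sentence | 4 | life threatening |
| Protocol Table 3, cited by that sentence | 5 | death |
| Protocol Appendix I, CTCAE v4.0 | 5 | not described |
| SAP 4.7.2 | CTCAE v4.0, no limit stated | not described |

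Only the recording sentence omits Grade 5, and it is the one that governs data entry.

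**Does anything later restore the grade?** SAP 4.7.2 has no rule that sets Grade 5 when an event was fatal and no reconciliation of severity tables with deaths. SAP Section 1 mentions separate Stage 1 and Stage 2 analysis plans by the previous sponsor. They were not available, so I cannot say whether they held such a rule.

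**What do the death tables cover?** Protocol 10.6.2 gives deaths by treatment, system organ class and preferred term, but does not specify relatedness for that table. SAP 4.7.2 gives deaths by treatment group. The SAP table by grade and relatedness is therefore the planned display that would show fatal events by relatedness, and it is one of those affected.

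**Effect on a table.** For one arm of n subjects, let f be those whose worst event was fatal, g the others with worst grade 4, and s the share of the f recorded as Grade 4.

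- Grade 4 shown = (g + s × f) / n
- Grade 5 shown = (1 − s) × f / n
- Sum = (g + f) / n, which does not depend on s

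For illustration only, take n = 84 / 3 = 28, f = 3 and g = 5. The values of f and g are assumed and do not come from the documents.

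| Fatal events recorded as Grade 4 | Grade 4 shown | Grade 5 shown |
|---|---|---|
| 0 of 3 | 5/28 = 17.9% | 3/28 = 10.7% |
| 1 of 3 | 6/28 = 21.4% | 2/28 = 7.1% |
| 2 of 3 | 7/28 = 25.0% | 1/28 = 3.6% |
| 3 of 3 | 8/28 = 28.6% | 0/28 = 0% |

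The total at Grade 4 or above is 8/28 in every row. Only the split between Grades 4 and 5 moves.

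**The case against.** The strongest reply is that this is a drafting slip with little reach. The paragraph names CTCAE as the reference and cites a table that prints Grade 5, so sites have conflicting text and not a ban. The eCRF is not among the documents, and its severity field may already offer Grade 5. The SAP grades by CTCAE without limiting it to four levels. Deaths are tabulated by preferred term and by arm, and the safety endpoint in Section 3.2 is incidence of events, with maximum severity as an added table. All of this stands, and it limits the point to the severity tables. It does not remove the conflict: two instructions for one field can give inconsistent data, and the SAP does not say how to handle them.

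A reader might infer more than the documents support:

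- **That fatal events cannot appear as fatal, or that all are misgraded.** This would need an eCRF without Grade 5, or every site following the sentence over the table it cites. Neither is shown.
- **That fatal terms are hidden.** Protocol 10.6.2 tabulates deaths by system organ class and preferred term within treatment.
- **That fatal events are lost among Grade 4 cytopenias.** The documents give no rate for these, and in tables by body system or term such mixing arises only within a shared row or in an overall worst-grade row.
- **That the SAP's no-query statement prevents correction.** It concerns discrepancies in MedDRA Preferred Terms after re-coding and does not address grades.

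**Conclusion.** The point holds in a limited form. The recording sentence in Protocol 7.13.1.3 contradicts Table 3 and Appendix I. Fatal adverse events may as a result be recorded as Grade 4, or inconsistently between sites. The tables by maximum severity and by CTCAE grade and relatedness may then understate Grade 5, overstate Grade 4 by the same number, and disagree with the death tabulations. Reporting of deaths themselves and counts at Grade 4 or above are not affected.

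The size is unknown, because it depends on the number of fatal events and on how the eCRF field was built. The conclusion assumes that at least some sites follow the sentence as written and that no derivation rule exists outside the supplied documents. It is worth correcting because the contradiction is plain and the correction costs almost nothing.

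**What to change.** 1. **Protocol 7.13.1.3.** Extend the recording sentence to Grade 5, death related to the adverse event, so that it matches Table 3. This is one phrase.
2. **eCRF.** Confirm that the severity field accepts Grade 5, and open it if it does not. This is one check and at most one option.
3. **SAP 4.7.2.** State that an adverse event that resulted in death is analysed as Grade 5, and that the severity tables are reconciled with the death listing before release. Fatal events can be identified from the death record or from the seriousness criterion, which Section 7.13.2.2 requires in the initial serious adverse event report. This is one derivation rule and one listing check.

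The third item matters most. SAP Section 1 places this SAP before the final lock of the extensions, with the primary locks covered by earlier plans, so a change to the protocol sentence would not correct grades already entered. These changes concern recording and analysis only and do not touch the management of subjects.
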